4.3 Primary, secondary and exploratory endpoints

Primary endpoints 4.3.1

Endpoint title	Time frame	Unit
For haemophilia A patients	On demand (arm 1)	Count
without inhibitors:	 From randomisation after the pause 	
	(week 0) up until start of concizumab	
The number of treated	treatment (week 24)	
spontaneous and traumatic		
bleeding episodes	Concizumab (arm 2)	
	• From start of the new concizumab dosing	
	regimen (week 0) up until the confirmatory	
	analyses cut-off (at least 32 weeks)	
For haemophilia B patients	On demand (arm 1)	Count
without inhibitors:	 From randomisation after the pause 	
	(week 0) up until start of concizumab	
The number of treated	treatment (week 24)	
spontaneous and traumatic		
bleeding episodes	Concizumab (arm 2)	
	• From start of the new concizumab dosing	
	regimen (week 0) up until the confirmatory	
	analyses cut-off (at least 32 weeks)	

Secondary endpoints 4.3.2

4.3.2.1 **Confirmatory secondary endpoints**

Endpoint title	Time frame	Unit
Effect		
For haemophilia A patients without inhibitors: The number of treated spontaneous and traumatic bleeding episodes	 Arm 4 patients who have been on stable PPX at least 24 weeks in study 4322 For previous PPX (study 4322): From the point in time where PPX is stable^a and up until the end of study. For concizumab PPX (trial 4307): From the point in time where the concizumab maintenance dose is confirmed, increased or decreased and up until the confirmatory analyses cut-off (at least 24 weeks). 	Count
For haemophilia B patients without inhibitors: The number of treated spontaneous and traumatic bleeding episodes	 Arm 4 patients who have been on stable PPX at least 24 weeks in study 4322 For previous PPX (study 4322): From the point in time where PPX is stable^a and up until the end of study. For concizumab PPX (trial 4307): From the point in time where the concizumab 	Count

Protocol		Date:	25 March 2021	Novo Nordisk
Trial ID: NN7415-4307	CONFIDENTIAL	Version:	5.0	

Status:

Page:

Final

35 of 138

maintenance dose is confirmed, increased or	
decreased and up until the confirmatory	
analyses cut-off (at least 24 weeks).	

CONFIDENTIAL

Supportive secondary endpoints 4.3.2.2

Endpoint title	Time frame	Unit
Effect		1
For haemophilia A patients without inhibitors: Number of treated spontaneous bleeding episodes	• From randomisation after the pause (week 0) up until start of concizumab treatment (week 24)	Count
	 Concizumab (arm 2) From start of the new concizumab dosing regimen (week 0) up until the confirmatory analyses cut-off (at least 32 weeks) 	
For haemophilia B patients without inhibitors: Number of treated spontaneous bleeding episodes	• From randomisation after the pause (week 0) up until start of concizumab treatment (week 24)	Count
	 Concizumab (arm 2) From start of the new concizumab dosing regimen (week 0) up until the confirmatory analyses cut-off (at least 32 weeks) 	
For haemophilia A patients without inhibitors: Number of treated spontaneous and traumatic joint bleeds	On demand (arm 1) • From randomisation after the pause (week 0) up until start of concizumab treatment (week 24)	Count
	 Concizumab (arm 2) From start of the new concizumab dosing regimen (week 0) up until the confirmatory analyses cut-off (at least 32 weeks) 	
For haemophilia B patients without inhibitors: Number of treated spontaneous and traumatic joint bleeds	On demand (arm 1) • From randomisation after the pause (week 0) up until start of concizumab treatment (week 24)	Count
	Concizumab (arm 2) • From start of the new concizumab dosing regimen (week 0) up until the confirmatory analyses cut-off (at least 32 weeks)	

^aStable is defined as the time after an initial period on PPX treatment of at least 24 weeks

Protocol Trial ID: NN7415-4307

CONFIDENTIAL

Date: Version: Status: Page: 5 March 2021 5.0 Final 36 of 138

Endpoint title	Time frame Uni	
For haemophilia A patients without inhibitors: Number of treated spontaneous and traumatic target joint bleeds	On demand (arm 1) • From randomisation after the pause (week 0) up until start of concizumab treatment (week 24)	Count
	 Concizumab (arm 2) From start of the new concizumab dosing regimen (week 0) up until the confirmatory analyses cut-off (at least 32 weeks) 	
For haemophilia B patients without inhibitors: Number of treated spontaneous and traumatic target joint bleeds	On demand (arm 1) • From randomisation after the pause (week 0) up until start of concizumab treatment (week 24) Concizumab (arm 2)	Count
	• From start of the new concizumab dosing regimen (week 0) up until the confirmatory analyses cut-off (at least 32 weeks)	
Safety		
Number of thromboembolic events	On demand (arm 1 main part) From randomisation to on demand treatment up until start of concizumab treatment ^d	Count
	 Concizumab (arms 2-4) Before the pause^b: From start of concizumab treatment (week 0^c) up until 7 weeks after the treatment was paused 	
	as well as	
	• After the pause ^b : From start of concizumab treatment (week 0 ^a) up until the confirmatory analyses cut-off (at least 32 weeks)	
	 Concizumab (arm 1 extension part) From start of concizumab treatment (visit 9a) up until the confirmatory analysis cut-off 	
Number of thromboembolic events	Oncizumab Before the pause ^b : From start of treatment (week 0 ^c) up until 7 weeks after the treatment was paused	Count

CONFIDENTIAL

Date: Version: Status: Page: 5 March 2021 5.0 Final 37 of 138

Endpoint title	Unit	
	 After the pause^b: From start of concizumab treatment up until the end of trial (week 167) 	
Number of hypersensitivity type reactions	On demand (arm 1 main part) • From randomisation to on demand treatment up until start of concizumab treatment ^d Concizumab (arms 2-4) • Before the pause ^b : From start of concizumab treatment (week 0°) up until	Count
	 7 weeks after the treatment was paused as well as After the pause^b: From start of concizumab treatment (week 0^a) up until the confirmatory analyses cut-off (at least 32 weeks) 	
	 Concizumab (arm 1 extension part) From start of concizumab treatment (visit 9a) up until the confirmatory analysis cut-off 	
Number of hypersensitivity type reactions	• Before the pause ^b : From start of treatment (week 0°) up until 7 weeks after the treatment was paused as well as	Count
	 After the pause^b: From start of concizumab treatment up until the end of trial (week 167) 	
Number of injection site reactions	On demand (arm 1 main part) • From randomisation to on demand treatment up until start of concizumab treatment ^d	Count
	 Concizumab (arms 2-4) Before the pause^b: From start of concizumab treatment (week 0^c) up until 7 weeks after the treatment was paused 	

CONFIDENTIAL

Date: Version: Status: Page: 25 March 2021 | **Novo Nordisk**5.0
Final
38 of 138

Endpoint title	Time frame	Unit
	 After the pause^b: From start of concizumab treatment (week 0^a) up until the confirmatory analyses cut-off (at least 32 weeks) Concizumab (arm 1 extension part) From start of concizumab treatment (visit 9a) up until the confirmatory analysis cut-off 	
Number of injection site reactions	 Concizumab Before the pause^b: From start of treatment (week 0°) up until 7 weeks after the treatment was paused as well as After the pause^b: From start of concizumab treatment up until the end of trial (week 167) 	Count
Number of patients with antibodies to concizumab	 Concizumab (arms 2-4) Before the pause^b: From start of concizumab treatment (week 0^c) up until 7 weeks after the treatment was paused After the pause^b: From start of concizumab treatment (week 0^a) up until the confirmatory analyses cut-off (at least 32 weeks) Concizumab (arm 1 extension part) From start of concizumab treatment (visit 9a) up until the confirmatory analysis cut-off 	Count

Protocol Trial ID: NN7415-4307

CONFIDENTIAL

Date: Version: Status: Page:

25 March 2021 5.0 Final 39 of 138

Endpoint title	Time frame	Unit
Number of patients with antibodies to concizumab	 Before the pause^b: From start of treatment (week 0^c) up until 7 weeks after the treatment was paused as well as After the pause^b: From start of concizumab treatment up until the end of trial (week 167) 	
Pharmacokinetic and pharm	acodynamic endpoints	
Pre-dose (trough) concizumab plasma concentration (C _{trough})	Prior to the concizumab administration at week 24 (after restart)	ng/mL
Pre-dose thrombin peak	Prior to the concizumab administration at week 24 (after restart)	nmol/L
Pre-dose free TFPI concentration	Prior to the concizumab administration at week 24 (after restart)	ng/mL
Maximum concizumab plasma concentration (C _{max})	From 0 to 24 hours where 0 is time of the concizumab dose at week 24 (after restart)	ng/mL
Area under the concizumab plasma concentration-time curve (AUC)	From 0 to 24 hours where 0 is time of the concizumab dose at week 24 (after restart)	ng*hr/mL

^aDefined as time of randomisation to on-demand administration after the pause or time of start of the new concizumab dosing regimen.

^bDefined as the pause in the concizumab clinical development programme during March to August 2020, while thromboembolic events were investigated.

^eDefined as time of the initial randomisation to on-demand administration or time of start of the previous concizumab dosing regimen (0.25 mg/kg/day).

^dSafety will be described separately for patients randomised to on demand treatment before the pause.

25 March 2021 5.0 Final 40 of 138

4.3.3 Exploratory endpoints

Endpoint title	Time frame	Unit
Patient reported outcomes		
Change in SF-36v2 bodily pain	From baseline (week 0 ^a) until week 24	Score
Change in SF-36v2 physical functioning	From baseline (week 0 ^a) until week 24	Score
Patient preference assessed by questionnaire	Week 24	%
Change in patient's treatment burden using the Hemo-TEM total score	From baseline (week 0 ^a) until week 24	Score
Change in PROMIS Short Form v2.0 -Upper Extremity 7a	From baseline (week 0 ^a) until week 24	Score
Change in PROMIS Numeric Rating Scale v.1.0 – Pain Intensity 1a	From baseline (week 0 ^a) until week 24	Score
Change in Haem-A-QoL total score	From baseline (week 0 ^a) until week 24	Score
Change in Haem-A-QoL physical health domain score	From baseline (week 0 ^a) until week 24	Score
Physical activity measured by	v accelerometer	 
Change in time spend in moderate to vigorous physical activity (MVPA) per day	From baseline to end of the main part (week 24 for the on-demand arm and week 32 for the concizumab arms)	Minutes per day

^aDefined as time of randomisation to on-demand administration after the pause or time of start of the new concizumab dosing regimen.

25 March 2021 Novo Nordisk 5.0 Final 41 of 138

5 Trial design

5.1 Overall design

This is a prospective, multicentre, open label clinical trial with two randomised arms and two nonrandomised arms. The trial aims to evaluate the effect and safety of daily concizumab prophylaxis administered s.c. in patients with HA and HB. Patients will be randomised to concizumab PPX or no PPX or assigned into the non-randomised treatment arms, based on their treatment regimen before entering the trial. Upon restart, patients who were randomised to arms 1 or 2 before the pause will enter arm 4. Patients who were allocated to arms 3 and 4 before the pause will re-enter the arm they were initially allocated to. The randomisation into arms 1 or 2 will be restarted with new patients. The main part of the trial is completed for a patient when the patient has completed 24 weeks of participation (screening period not included) for patients in arm 1 or 32 weeks of participation (screening period not included) for patients in arms 2,3 and 4. After the main part of the trial, all patients will be offered to continue in the extension part of the trial and receive treatment with concizumab for up to an additional 128 weeks (arms 2–4) or 136 weeks (arm 1) (Figure 1).

A confirmatory analyses cut-off will be defined as when all patients in arm 1 have completed visit 9a (or withdrawn) and all patients in arms 2 and 4 have completed visit 10a (or withdrawn). This will ensure that all patients in arms 2 and 4 have completed the dose adjustment period and at least an additional 24 weeks of concizumab PPX on their final maintenance dose (or withdrawn). Furthermore, a 56-week cut-off is defined as when all patients in arms 2, 3 and 4 have completed visit 13a (or permanently discontinued treatment). At this 56-week cut-off, an additional evaluation will be made assessing bleed related endpoints and safety.

[figure not shown]
After up to 128/136 weeks in extension part the patient will enter the safety follow-up part of the trial. The patient will receive his last dose at home on the day prior to visit 26a. The follow-up part of the trial lasts for 7 weeks and the patient will continue to report bleeding episodes until visit 27a.

In this version of the protocol, patients not already enrolled at the time of the re-start, will be defined as new patients recruited from the non-interventional study NN7415-4322 (explorer 6) and from outside the concizumab programme. New patients can belong to the following categories:

- patients who previously participated in NN7415-4255 (explorer 5)
- patients who were in screening phase at the time of the pause
- patients entering from NN7415-4322 (explorer 6)
- new patients coming from outside the concizumab programme.

All of the above-mentioned new patients will start the trial at visit 1a (screening visit).

5.0 Final 42 of 138

Note: ^aThe individual maintenance dose will be either 0.15, 0.20 or 0.25 mg/kg concizumab (see Section 9.2.2); ^bAdditional patients on OnD treatment or patients on PPX with factor replacement, patients from explorer5 enrolled *after* the treatment pause and patients randomised to arms 1 or 2 *before* the treatment pause.

Abbreviations: OnD = on demand; PPX = prophylaxis; V = visit

Figure 1 Trial design

The randomisation between the treatment arms 1 and 2 will be stratified according to haemophilia type and bleeding frequency during the 24 weeks prior to screening; see Section 7.2.

Treatment arms 1 and 2:

Approximately 60 patients (24 HA and 36 HB patients), previously treated on-demand, will be randomised 1:2 to no prophylaxis versus concizumab prophylaxis.

Patients randomised to arm 1 before the pause were instructed to continue their on demand treatment and report data until trial restart. Patients who were randomised to arms 1 and 2 prior to the treatment pause should re-enter the trial in arm 4. Instead 60 new patients will be identified to be randomised into arms 1 or 2.

Treatment arm 3:

The HA patients enrolled into the concizumab phase 2 trial NN7415-4255 (explorer 5) were offered enrolment into arm 3. These patients continued concizumab PPX and had a combined visit 1 and 2. Upon trial restart, these patients will receive the new concizumab dosing regimen. After the initial dose adjustment period, patients will receive at least 24 weeks of treatment on their final maintenance dose (main part). Subsequently, these patients will be offered up to 128 weeks of concizumab PPX (extension part).

Patients who were in NN7415-4255 (explorer 5) at the time of the treatment pause, and who have now completed explorer 5, will be offered screening in this trial and should enter arm 4 (visit 1a) as outlined below.

Page:

43 of 138

Treatment arm 4:

Arm 4 will include at least 60 patients (30 HA and 30 HB patients) previously on prophylaxis with factor products with a minimum of 24 weeks observation in NN7415-4322 (explorer 6).

In addition, arm 4 will also include:

- Patients who were randomised to arms 1 and 2 before the treatment pause
- HA patients who were in NN7415-4255 (explorer 5) at the time of the treatment pause, and who have now completed explorer 5
- On demand patients included after arms 1 and 2 are closed

Patients who were enrolled before the pause

Patients who were randomised or allocated to treatment in this trial before the pause, should re-enter the trial as outlined in Table 1.

Table 1 Visit overview for patients restarting this trial

Allocation before the pause	Allocation at restart
Arm 1	Arm 4 - visit 2a
Arm 2	Arm 4 - visit 2a
Arm 3	Arm 3 - visit 2a
Arm 4	Arm 4 - visit 2a

Table 2 below summarises the expected numbers of randomised/enrolled patients in each arm. In total 158 patients are expected to be enrolled. The aim is to have approximately 21 HA and 14 HB unique adolescent patients defined as patients between ≥ 12 to < 18 years at trial start.

Table 2 Randomisation/enrolment overview

	Minimum number of patients randomised/enrolled				
	Arm 1	Arm 2	Arm 3	Arm 4 Minimum number of PPX patients from NN7415-4322 (explorer 6) with at least 24 weeks observation period on stable PPX	
НА	8	16	10	30	
НВ	12	24	N/A	30	

Note: In addition to the 60 patients needed for the confirmatory secondary analysis (within-patient comparison), arm 4 will also include patients who were randomised to arms 1 or 2 before the treatment pause, HA patients from NN7415-4255 (explorer 5) included after the treatment pause as well as on demand patients included after arms 1 and 2 are closed.

5.2 Treatment of patients

[figure not shown]
5.2.1 Concizumab prophylaxis

When patients are randomised/allocated to concizumab prophylaxis, they will receive a loading dose of 1.0 mg/kg concizumab at visit 2a (arm 2, 3 and 4) or visit 9a (arm 1) followed by an initial daily dose of 0.20 mg/kg concizumab from treatment day 2. Within an initial 5–8-week dose adjustment period on 0.20 mg/kg concizumab, the patients can be increased or decreased in dose to 0.25 mg/kg or 0.15 mg/kg concizumab. A potential dose adjustment will take place at visit 4a.1 or

Page:

44 of 138

9a.3 and will be based on the concizumab exposure level measured at the previous visit 4a or 9a.2. Patients who have concizumab exposure levels of 200–4000 ng/mL will stay at 0.20 mg/kg concizumab. The new concizumab dosing regimen is shown schematically in Figure 2 and explained in further detail in Section 9.2.2.

Abbreviation: LD = loading dose

Notes: Concizumab exposure level is measured at V4a/9a.2; Potential dose adjustment will take place at V4a.1/9a.3.

Figure 2 Concizumab dosing regimen upon re-initiation of trial

Doses, including the loading dose, given at PK/PD visits (i.e. visit 2a and 9a) will be administered at the site; all other injections may be administered at home by the patient or caregiver.

Prior to visit 2a, patients must be in a non-bleeding state 48 hour prior to the visit however patients can have treatment for up to 24 hours prior to visit 2a, except for treatment with aPCC and ByClot® where the wash-out is 48 hours prior to visit 2a. For patients coming from a PPX treatment regimen, an interval of 2 half-lives from the given factor product to first concizumab dose is required.

A pre-filled, multi-dose pen-injector for the drug administration will be provided by Novo Nordisk, details can be found in Section 7.1.1.

Use of factor-containing products not associated to a bleed is not allowed, except for diagnostic procedures, intramuscular injections (e.g. vaccinations) and minor surgery, e.g. dental treatment, endoscopies etc.

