Footnote a) Phone visit is allowed for patients randomised to arm 1 (on-demand patient) Week 0 is the time of trial restart c) Visit will take place after the concizumab exposure levels are available according to Section 9.2.2 d) Only patients enrolled in the trial after the treatment pause, will sign the Informed Consent at visit 1a e) Only patients enrolled in the trial before the treatment pause, will re-consent at visit 2a Only applicable for patients in arm 1, who are receiving concizumab at visit 9a g) Only applicable for patients in arm 2, 3 and 4, who are receiving concizumab at visit 2a h) Only applicable for patients enrolled in the trial before treatment pause. Site must ensure patients do not violate discontinuation criteria according to Section 8 before reinitiating dosing with concizumab. Patients randomised to arm 1 and 2 before the treatment pause will not be re-randomised at visit 2a Weight only, except at visit 1 where height is measured k) For patients having concizumab dosing at visit 2a there will be a 24-hour PK session at visit 2a and 9a. Please see details for PK sampling in Section 2.1. For on-demand patients (arm 1) only the pre-dose sample will be taken 1) Sample is taken pre-dose. Patients must not inject trial medication on this visit day before the sample is taken. m) Concizumab plasma concentration for dose adjustment (visit 4a for arm 2-4 and visit 9a.2 for arm 1) will be analysed using the concizumab ELISA in vitro diagnostic (IVD) device n) Only one sample to be taken, either factor VIII for HA patients or factor IX for HB patients o) Only applicable for patients having site visit due to dose-escalation Only for patients above ≥17 years old (at visit 1a) q) Only applicable for patients enrolled in the trial before the treatment pause r) Site visit must be performed in case of dose escalation. Phone visit is allowed for patients having dose de-escalation or dose unchanged. See Section 9.2.2 for further details A separate Informed Consent Form must be signed before any samples are taken. See Section 9.7 for further details Whole blood for DNA is only taken at screening

Protocol	Date:	25 March 2021	Status:	Final	Novo Nordisk
Trial ID: NN7415-4307	Version	: 5.0	Page:	26 of 138	

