4.1.2 Secondary objectives

- To compare the effect of concizumab prophylaxis to the patients' previous prophylaxis treatment in reducing the number of bleeding episodes in adult and adolescent patients with haemophilia A without inhibitors
- To compare the effect of concizumab prophylaxis to the patients' previous prophylaxis treatment in reducing the number of bleeding episodes in adult and adolescent patients with haemophilia B without inhibitors
- To investigate the safety of concizumab prophylaxis in adult and adolescent patients with haemophilia A or B without inhibitors
- To investigate the PK and PD parameters of concizumab prophylaxis in adult and adolescent patients with haemophilia A or B without inhibitors

4.1.3 **Exploratory objectives**

- To compare the patient-reported outcomes (PRO) in adult and adolescent patients with haemophilia A or B without inhibitors treated with concizumab prophylaxis to the PROs in patients treated with no prophylaxis
- To explore treatment preference for concizumab prophylaxis versus no prophylaxis or previous prophylaxis treatment in adult and adolescent patients with haemophilia A or B without inhibitors

4.2 **Estimands**

The five components of the estimand for the primary objective for HA patients are as follows:

- **Endpoint:**
- On demand (arm 1): The number of treated spontaneous and traumatic bleeding episodes from randomisation after the pause (week 0) up until start of concizumab treatment (week 24)
- Concizumab (arm 2): The number of treated spontaneous and traumatic bleeding episodes from start of the new concizumab dosing regimen (week 0) up until the confirmatory analyses cut-off (at least 32 weeks)
- Treatment regimens: Either a) on demand treatment with intravenous replacement with factorcontaining products, or b) PPX treatment regimen with subcutaneous concizumab consisting of an initial loading dose of 1.0 mg/kg, followed by an initial daily dose of 0.20 mg/kg (during the dose adjustment period), followed by a maintenance dose of either 0.15, 0.20 or 0.25 mg/kg

Status:

Final 32 of 138

where breakthrough bleeds are treated with intravenous replacement with factor-containing products.

- **Population-level summary**: The treatment ratio of the ABRs between the two randomised treatment regimens.

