5.2.2 On-demand treatment

Patients in arm 1 will continue on-demand treatment with their usual replacement therapy until visit 9a (end of main part). Novo Nordisk will not provide or reimburse on-demand treatment for patients in arm 1. In the extension part, patients in arm 1 will receive daily concizumab subcutaneous injections (see Section 5.2.1).

As noted in Section 5.1, Patients randomised to arm 1 before the pause will go to arm 4 upon restart of the trial. Thus, additional patients will be randomised to arm 1 (and 2) when restarting the trials.

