5.2.3 Treatment of break-through bleeding episodes

The patient must contact the site when they have a suspected bleed, see Section 9.2.3 for further details.

Date: Version: Status:

25 March 2021 Novo Nordisk 5.0 Final 45 of 138

Novo Nordisk will not provide or reimburse treatment for bleeding episodes. Any bleeds occurring in the trial can be treated with the patient's usual factor-containing product, taking the treatment guidance in Appendix 11 into consideration. Table 3 provides a tabular overview of the guidance on management of mild and moderate bleeds. Prophylactic treatment with concizumab should continue independent of bleeding episodes and their treatment, i.e. the original dosing schedule should be maintained unless investigator judges otherwise.

For treatment of bleeds, the dose must not exceed a single dose of 50 U/kg aPCC (FEIBA®), and not exceed 100 U/kg within 24 hours. The first treatment should be at the hospital, with observation of the patient for a minimum of 24 hours. If there are no safety concerns, the patient can continue with FEIBA® treatment for breakthrough bleeds at home. Single dose home treatment must not exceed 50 U/kg. If an additional dose is needed because a single dose was insufficient to treat the bleed, the patient must come to the site.

For treatment of bleeds, the dose must not exceed 60 µg/kg ByClot[®], and not exceed 90 µg/kg ByClot® within 24 hours. Additional dose can be given at an interval of 8 hours or longer. The first treatment should be at the hospital, with observation of the patient for a minimum of 24 hours. If there are no safety concerns, the patient can continue with ByClot® treatment for breakthrough bleeds at home. Single dose home treatment must not exceed 60 µg/kg. If an additional dose is needed because a single dose was insufficient to treat the bleed, the patient must come to the site.

Table 3 Guidance on management of mild and moderate bleeds during concizumab PPX

	FVIII SHL	FVIII EHL	FIX SHL	FIX EHL	rFVIIa	aPCC	ByClot®
Contact centre (PI)							
First dose ^a	20 IU/kg	20 IU/kg	30 IU/kg	30 IU/kg	90 μg/kg	Single dose must not exceed 50 U/kg, and not exceed 100 U/kg within 24 hours	Single dose must not exceed 60 µg/kg ByClot®, and not exceed 90 µg/kg ByClot® within 24 hours
Second dose	20 IU/kg	20 IU/kg	30 IU/kg	At investigator's discretion	90 μg/kg	At investigator's discretion	Additional dose can be given at an interval of 8 hours or longer

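### Section 5.2.1 ties three pre-dose bleeding and wash-out conditions to visit 2a only, so none of them applies when arm 1 takes its first concizumab dose at visit 9a

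*Protocol*

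**What the plan says.** Section 5.2.1 of the protocol names two first-dose visits. The loading dose is given as "concizumab at visit 2a (arm 2, 3 and 4) or visit 9a (arm 1"). Three conditions follow in the same section:

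- **Bleeding state:** "Prior to visit 2a, patients must be in a non-bleeding state 48 hour prior to the visit".
- **Prior treatment:** allowed up to 24 hours before visit 2a.
- **aPCC and ByClot:** an exception to the 24-hour allowance, "where the wash-out is 48 hours prior to visit 2a".

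A fourth rule, an interval of two half-lives, is attached to the first concizumab dose and not to a visit. It covers only patients coming from prophylaxis.

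Section 5.2.2 describes arm 1: "Patients in arm 1 will continue on-demand treatment with their usual replacement therapy until visit 9a (end of main part"). It then refers back for the dosing: "In the extension part, patients in arm 1 will receive daily concizumab subcutaneous injections (see Section 5.2.1").

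**The concern.** Arm 1 is the only arm whose first concizumab dose is not at visit 2a. It is also an arm in which factor may have been used shortly before that dose, because on-demand treatment runs until visit 9a. The three conditions therefore apply to arm 1 at randomisation, 24 weeks before any concizumab, and lapse when it receives the same loading dose as the other arms.

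A site following the text could give the loading dose during a bleed or within hours of a factor infusion. The same section does not allow that at visit 2a. The protocol does not state the reason for the rule, but Section 3.3 gives the context. All three patients with thromboembolic events had used breakthrough treatment just before symptoms began, and all events fell within three months of starting concizumab. One of the changes listed there is that previous prophylaxis may no longer overlap with the start of concizumab.

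**Working it through.** This is mainly a check of text; the plan gives no figure to reproduce.

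**1. What each rule in Section 5.2.1 is attached to**

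| Rule | Attached to | Reaches arm 1 at visit 9a? |
|---|---|---|
| 48 h non-bleeding state | Visit 2a | No |
| 24 h limit on prior treatment | Visit 2a | No |
| 48 h aPCC/ByClot wash-out | Visit 2a | No |
| Two half-lives of factor product | First concizumab dose, patients from prophylaxis | No, by design |

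The last row is not a defect. Arm 1 comes from on-demand treatment, and Section 4.2 counts starting prophylaxis in that arm as permanent treatment discontinuation.

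**2. Whether another section fills the gap**

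- Section 8.1.1 postpones the first dose for COVID-19 and names visits 2a and 9a.
- Section 9 requires consent before arm 1 starts concizumab.
- Appendix 11 requires bleed-management training before the first dose and names visit 2a for arms 2–4 and visit 9a for arm 1.
- The Section 2 flowchart schedules bleeding episodes, coagulation parameters and the discontinuation criteria at visit 9a.

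None of these sets a bleeding-state or wash-out condition. Nor do the eligibility and randomisation criteria, the list of prohibited medication, Section 8.1, Section 9.5 or the week-56 SAP. First-dose visits named: two. Visits to which the three conditions apply: one.

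**3. How often the situation could arise (illustrative)**

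Inputs: 8 HA and 12 HB patients in arm 1 (Table 2); on-demand ABRs of 24 and 18 (Section 10.1). Assuming a constant Poisson rate, the chance of at least one bleed starting within *d* days is 1 − exp(−ABR × *d* / 365.25).

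- 48 h, HA: 1 − exp(−24 × 2/365.25) = 0.1231. HB: 1 − exp(−18 × 2/365.25) = 0.0939.
- Expected number: 8 × 0.1231 + 12 × 0.0939 = 2.11 of 20. If 85% cross over (Section 10.1 expects less than 15% to stop early), about 1.8.
- 24 h: 8 × 0.0636 + 12 × 0.0481 = 1.09 of 20.
- Low case for 48 h, 10 bleeds in 52 weeks (Section 6.4): 20 × 0.0535 = 1.07.
- High case for 48 h, Table 15 values of 32.35 (HA) and 17.6 (HB): 8 × 0.1623 + 12 × 0.0919 = 2.40.

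**4. What correcting the rule would do to arm 1's observation time**

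Arm 1's endpoint counts "bleeding episodes from randomisation after the pause (week 0) up until start of concizumab treatment (week 24") (Section 4.2), so moving visit 9a lengthens the period. Planned time is 20 × 168 = 3,360 patient-days. Suppose every patient with a bleed starting in the 48 h window is delayed by two days:

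- HA: 8 × 0.1231 × 2 = 1.97 of 1,344 days (0.147%). HB: 12 × 0.0939 × 2 = 2.25 of 2,016 days (0.112%).
- Total: 4.22 / 3,360 = 0.126%. An assumed four-day delay gives 8.45 / 3,360 = 0.251%.
- If all the days added by a two-day delay were bleed-free, the ABR would fall to 24/1.00147 = 23.96 (HA) and 18/1.00112 = 17.98 (HB).

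**The case against.** The strongest reply is that the intent can be recovered. Section 5.2.2 sends arm 1's dosing to Section 5.2.1, other start-of-concizumab safeguards cover both visits, and a sensible site would carry the conditions over. That makes a deliberate exemption of arm 1 unlikely, and a reader should not infer one. It does not cure the text: the cross-reference leads to sentences that still say visit 2a, a visit arm 1 also attends, so they can be followed literally without any sign that something is missing.

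Second, factor is not forbidden alongside concizumab. Section 5.2.3 says "Prophylactic treatment with concizumab should continue independent of bleeding episodes and their treatment", and Table 3 handles concurrent use by dose guidance. The visit 9a dose is given on site, and the investigator may stop trial product for safety at any time. These points stand and keep the reach small. They do not explain why the first dose carries a stricter condition in arms 2–4 and none in arm 1, and they give site staff no criterion for delaying the dose.

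Third, the aPCC/ByClot part will rarely apply, because patients with inhibitors are excluded. The protocol's summary of changes also describes the wash-out clarification as being for patients on prior prophylaxis. That hints at intent for the wash-out, but it does not touch the non-bleeding condition.

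A reader might infer from Section 3.3 that arm 1 is exposed to a known thrombotic risk. The documents do not support that. They report breakthrough treatment before symptoms in patients already on concizumab, under the previous dosing regimen. They say nothing about factor given before a first dose and allow no estimate of harm.

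**Conclusion.** The concern holds as a minor safety and conduct correction. Section 5.2.1 is wrong as written: for arm 1, three pre-dose conditions are tied to the wrong visit, and no other section supplies them at visit 9a. This rests on the text alone. Figures 1–3 are not shown in the copy reviewed, but their visible notes contain no such condition.

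Three stronger readings should be set aside:

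- **That four conditions are missing.** The half-life interval is already tied to the first dose and leaves out arm 1 correctly. The gap is three.
- **That about 2 of 20 patients would breach the rule.** The figure counts bleeds starting in the window. It omits earlier bleeds still in progress, and a bleed starting within 24 hours is not the same as treatment within 24 hours. On-demand patients from explorer 6 have no minimum bleed count, so their rate could be lower. The range of about 1.1 to 2.4 of 20 shows only that the situation is plausible.
- **That the primary comparison is compromised.** Arm 1's bleeds are counted only until concizumab starts, so the gap lies after its endpoint period.

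**What to change.** Reword the sentence in Section 5.2.1 along these lines:

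*Before visit 2a (all arms) and before visit 9a (arm 1), patients must be in a non-bleeding state 48 hours before that visit. Treatment is allowed up to 24 hours before that visit, except aPCC and ByClot, for which the wash-out is 48 hours before that visit.*

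Keep visit 2a for all arms. New patients in arms 1 and 2 learn their arm there, and all others are dosed there. If the conditions are not met, reschedule visit 9a, within its ±3-day window where possible. Section 8.1.1 already postpones that visit for COVID-19. An explicit rescheduling clause is useful but optional; naming visit 9a is the essential change.

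The cost is one sentence of protocol text and a letter to sites. The downside is an occasional short delay to crossover, which makes the end of arm 1's observation period slightly dependent on recent bleeding. The exposure offset does not remove that dependence, but at about 0.13% of patient-days for two-day delays it is negligible. If the added days were bleed-free, it would work slightly against concizumab.
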